# 8.4.2. Sample Collection for Biomarkers in Blood

Blood samples for analysis of NE, CatG, PR3 and other neutrophil functions will be collected at the following time points:

- Screening Visit
- 0 hour (predose) on Day 1, Week 4, Week 16, Week 28, Week 40, and Week 52
- At Week 56 (Follow-up Visit)

# 8.5. Pharmacokinetic-Pharmacodynamic Endpoints

Pharmacokinetic-efficacy relationships (eg, PEs and concentrations of active NE in sputum) will be explored using a population PK-PD approach.

Pharmacokinetic-safety relationship (eg, AESI) will be explored using a population PK-PD approach.

The analysis plan will be described in a PK/PD SAP.

# 9. ASSESSMENT OF SAFETY

# 9.1. Vital Signs and Pulse Oximetry

Five-minute sitting BP (systolic and diastolic blood pressures), pulse rate (bpm), body temperature (°C), respiration rate (breaths per minute), and oxygen saturation will be recorded in the eCRF at the Screening Visit, and at all in-clinic study visits, as specified in the Schedule of Assessments (Table 5).

# 9.2. Physical Examination, Height, and Weight

A physical examination of the head (external), eyes, ears, nose and throat, lungs, cardiovascular system, abdomen, musculoskeletal system, skin, lymph nodes, central nervous system, and, as appropriate, other body systems will be performed during the Screening Visit (Visit 1) and at Week 52 (Table 5). Any abnormalities noticed at Screening will be recorded in the medical history or as AE if occurred after randomization. The physical examination will also include measurement of height, body weight, and calculation of BMI. Body weight will be measured at the Screening Visit (Visit 1) and at the Week 52 Visit (Visit 11; EOT). For adult subjects, the measurement of height, without shoes, will be performed at the Screening Visit only. For adolescent subjects, measurement of height, without shoes, will be performed at the Screening Visit and Visit 11 (EOT).

# 9.3. Chest CT Scan

A high-resolution chest CT scan will be performed at the Screening Visit if the subject does not have prior radiological confirmation of NCFBE diagnosis or if the available CT scan was obtained more than 5 years prior to the subject's Screening Visit or the existing CT scan cannot be read due to quality issues (Table 5). A prior chest CT scan may be used if this CT scan was obtained within 5 years from the subject's Screening Visit.

# 9.4. Electrocardiogram

A 12-lead ECG will be performed at Screening, Baseline, Weeks 4, 28, 40, and 52 (EOT) (Table 5). It is recommended to obtain the 12-lead ECG before PFT by spirometry when scheduled at the same visit.

# 9.5. Clinical Laboratory Assessments

Clinical laboratory tests of hematology, blood chemistry, and urinalysis will be performed via the study-designated laboratory at the Screening Visit, Baseline, and at all in-clinic study visits, as specified in the Schedule of Assessments (Table 5). The clinical laboratory test parameters are listed in Table 6.

**Table 6: Clinical Laboratory Parameters** 

Category	Laboratory Parameters
Clinical Chemistry	Sodium, chloride, potassium, CO 2 , magnesium, calcium, glucose, phosphate, total bilirubin (with direct and indirect fractionation, if total bilirubin is elevated > 2 × ULN), alkaline phosphatase, LDH, AST, ALT, albumin, total protein, creatinine, urea-nitrogen, uric acid, estimated glomerular filtration rate from the Chronic Kidney Disease - Epidemiology Collaboration equation formula (described in Section 9.9)
Hematology	Hemoglobin, erythrocytes, hematocrit, MCH, MCV, MCHC, leukocytes, differential blood count of neutrophils, eosinophils, basophils, monocytes, lymphocytes, and platelets
Urinalysis	Qualitative analysis of glucose, ketones, nitrites, protein, pH, leukocytes, blood, bilirubin, specific gravity; microscopic examination for cells, casts, and bacteria
Special Tests	For WOCBP ≤45 years, a testing of FSH level is required at Screening; a threshold of >40 mIU/mL should be met to be considered infertile

ALT=alanine aminotransferase, AST=aspartate aminotransferase, CO2=carbon dioxide, FSH=follicle-stimulating hormone, LDH=lactate dehydrogenase, MCH=mean corpuscular hemoglobin, MCHC=mean corpuscular hemoglobin concentration, MCV=mean corpuscular volume, ULN=upper limit of normal, WOCBP=women of childbearing potential.

# 9.6. Dental Hygiene Education

Dental hygiene education includes instruction in daily brushing and flossing. Subjects will be reminded at every visit on the need to maintain an appropriate dental hygiene.

If there are any signs or symptoms of gingivitis or periodontitis that warrant further evaluation upon Investigator discretion, the subject will be referred to a dentist/periodontist for further assessment. The oral and dental evaluation by the dentist for the subject should be assessed thereafter on an interval per the dentist's discretion until EOS Visit.

# 9.7. Serology Tests

Testing for HBcAb, HBsAb, HBsAg, HIV, and HCV will be conducted at Screening only.

# 9.8. Serum or Urine Pregnancy Test

A serum pregnancy test will be performed on WOCBP at Screening. A urine pregnancy test will be performed on WOCBP on Day1 (Baseline) and all other visit days, as specified in the Schedule of Assessments (Table 5). In addition to the pregnancy tests required by the Schedule of Assessments, monthly urine pregnancy tests should be conducted by WOCBP in countries where it is required by a local health authority. Adolescent female subjects who reach menarche during the course of the study should undergo urine pregnancy testing at the next clinic visit and at all following clinical visits (monthly where required by local health authority).

Please note that for days of Phone Visits (and monthly home tests, where applicable), WOCBP will be provided with urine pregnancy kits; the test should be performed at home on the day of the Phone Visit (or on the scheduled monthly frequency, where applicable) and the results reported to the site.

Women not of childbearing potential are defined as pre-menarche, postmenopausal (ie, amenorrheic for at least 1 year), or surgically or naturally sterile.

## 9.9. Estimated Glomerular Filtration Rate

The eGFR calculation per CKD-EPI equation will be analyzed for each subject at Visit 1 (Screening) and at Week 16, Week 28, and Week 52 (EOT).

The CKD-EPI equation described below will be used to calculate the eGFR of creatinine clearance in mL/min.

GFR =  $141 \times min (Scr/\kappa, 1) \alpha \times max (Scr/\kappa, 1)-1.209 \times 0.993$  Age  $\times 1.018$  [if female]  $\times 1.159$  [if Black]

where:

Scr is the serum creatinine in mg/dL,  $\kappa$  is 0.7 for females and 0.9 for males,  $\alpha$  is -0.329 for females and -0.411 for males, min indicates the minimum of Scr/ $\kappa$  or 1, max indicates the maximum of Scr/ $\kappa$  or 1.

### 9.10. Adverse Events

The Investigator is responsible for detecting, documenting, and reporting AEs (refer to Section 9.10.1 and Section 9.10.2 for the definition of AEs and SAEs, respectively).

The Investigator remains responsible for following up all AEs. At the EOS Visit, the Investigator will record the AE status (stable or unstable) in the eCRF.

#### 9.10.1. Definition of an Adverse Event

An AE is defined as any untoward medical occurrence in a subject or clinical investigation subject administered a pharmaceutical product and which does not necessarily have to have a causal relationship with this treatment. An AE can therefore be any unfavorable and unintended sign (including an abnormal laboratory finding, for example), symptom, or disease temporally associated with the use of a medicinal product, whether or not considered related to the medicinal product (ICH E2A Guideline. Clinical Safety Data Management: Definitions and Standards for Expedited Reporting, October 1994). Protocol-defined PEs (Section 7.1) are collected as efficacy endpoints via the eCRF. These events should not be reported as AEs unless they fulfill a seriousness criterion.

It is the responsibility of Investigators, based on their knowledge and experience, to determine those circumstances or abnormal laboratory findings that should be considered AEs.

#### 9.10.2. Definition of a Serious Adverse Event

Any untoward medical occurrence that at any dose:

- Results in death,
- Is life-threatening,

- Requires inpatient hospitalization or prolongation of existing hospitalization,
- Results in persistent or significant disability/incapacity,
- Is a congenital anomaly/birth defect, or
- Is an important medical event

Note: The term "life-threatening" in the definition of "serious" refers to an event in which the subject was at risk of death at the time of the event; it does not refer to an event which hypothetically might have caused death if it were more severe (ICH E2A Guideline. Clinical Safety Data Management: Definitions and Standards for Expedited Reporting, October 1994).

Medical and scientific judgment should be exercised in deciding whether expedited reporting is appropriate in other situations, such as important medical events that may not be immediately life-threatening or result in death or hospitalization but may jeopardize the subject or may require intervention to prevent one of the other outcomes listed in the definition above. Examples include allergic bronchospasm, convulsions, and blood dyscrasias or development of drug dependency or drug abuse.

#### Note:

- A procedure is not an AE or SAE, but the reason for the procedure may be an AE or SAE.
- Pre-planned (prior to signing the ICF) procedures or treatment requiring hospitalizations for pre-existing conditions that do not worsen in severity are not SAEs.

## 9.10.3. Adverse Event of Special Interest

AESIs are defined as events known as related to treatment with DPP1 inhibitors. Additional information on AESIs will be collected in the eCRF. The AESI category groups and preferred terms include the following: hyperkeratosis, infection, and periodontal/gingival events.

## 9.10.3.1. Hyperkeratosis

The subjects' skin will be monitored throughout the study.

At each study visit the Investigator (or designated healthcare professional in case of a public health emergency) will perform a careful skin evaluation, especially of the palmar and plantar surfaces, the dorsal surfaces of the hands and feet, the Achilles tendon area, knees, and elbows. If there are any signs or symptoms of hyperkeratosis or erythema or deterioration of the pre-existing conditions that warrant further evaluation upon Investigator discretion, the subject will be referred to a dermatologist for further assessment. The skin evaluation by the dermatologist for the subject should then be assessed thereafter on an interval per the dermatologist discretion until the end of the study.

Skin exfoliation or signs of skin thickening in the palms, soles, dorsum of the hands and feet, Achilles tendon area, knees, or elbows should always warrant evaluation by the dermatologist.

Decisions to discontinue the subject from the study will be made by the Investigator after consulting with the dermatologist. Upon receiving the dermatologist's evaluation, the

Investigator should decide whether to continue the subject in the study or initiate early discontinuation of the subject.

# 9.10.3.2. Periodontitis/Gingivitis

Adult subjects will be advised to conduct self-monitoring of their oral soft tissue, gingiva, and tooth mobility, and report any findings. For adolescents, oral and dental inspection for any signs or symptoms of gingivitis or periodontitis will be performed by the Investigator at each visit.

Occurrence of periodontitis during the study will be considered an AESI. If there are any signs or symptoms of periodontitis or gingivitis that warrant further evaluation upon Investigator discretion, the subject will be referred to a dentist/periodontist for further assessment and treatment. Subjects will be discontinued from the trial if they develop severe periodontal disease as defined by:

- Pocket depth measurement and attachment loss ≥6 mm on 2 or more teeth
- Have Class 3 mobility or Class 3 furcation involvement

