# 4.2. Discontinuation of Study Treatment and Participant Discontinuation/Withdrawal

### 4.2.1. Discontinuation of Study Treatment

All subjects are encouraged to stay in the study regardless of study treatment discontinuation. Any subject who discontinues from the study treatment will have the reason for discontinuing treatment recorded and will be encouraged to continue to attend the remaining scheduled study visits and to complete patient-reported outcome measures assessed between study visits (Table 5, Section 7.5).

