#### 4.2.2.1. Reasons for Withdrawal/Early Discontinuation

A subject may decide to withdraw from the study at any time, for any reason, without prejudice to subsequent care or treatment by the Investigator. When this occurs, the subject should complete all the procedures for the Week 52 (EOT) Visit. Subjects who discontinue the treatment due to AEs should remain under observation until the resolution or stabilization of the AEs. A subject may be discontinued from the study drug treatment before completion for any of the following reasons:

- 1. Subject death
- 2. Subject experiences an AE(s)/SAE(s) that warrants discontinuation, as judged by the Investigator and/or Insmed Medical Director
- 3. A major protocol deviation, which, in the opinion/discretion of the Investigator and/or Insmed, compromises the data integrity of the study
- 4. Subject is noncompliant with the study drug treatment (defined as <80% compliance after at least 2 reeducation efforts)
- 5. Withdrawal by subject
- 6. Termination of the study by the Sponsor
- 7. Investigator discretion
- 8. Subject lost to follow-up
- 9. Subject pregnancy
- 10. Periodontal criteria met (see Section 9.10.3.2)
- 11. Skin criteria met (see Section 9.10.3.1)
- 12. Diagnosis of a malignancy during study, excluding carcinoma in situ of the cervix, or squamous or basal cell carcinoma of the skin
- 13. Serious infection, defined as any infection other than associated with a pulmonary exacerbation that:
  - a. Requires parenteral treatment with an antibiotic requiring admission to the hospital, or parenteral treatment with an antifungal, antiviral, antiparasitic, or antiprotozoal agent
  - b. Is opportunistic, such as TB or other infections whose nature or course may suggest an immunocompromised status
- 14. Subjects who develop neutropenia defined as ANC <1000/mm^3
- 15. Subjects who have the following:
  - a. ALT and/or AST values >3 × ULN and total bilirubin >2 × ULN, excluding confirmed Gilbert's Syndrome
  - b. Confirmed AST and/or ALT >5 × ULN (for more than 2 weeks).

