Except for those subjects who withdraw consent, die, or are lost to follow-up, subjects who discontinue their assigned study drug will be encouraged to continue to participate in their remaining scheduled study visits. Every effort should be made by the Investigator to keep these subjects in the study through Visit 11. "Lost to follow-up" should be marked only in an exceptional case when all documented attempts to reach the subject by the Investigator or other staff members were unsuccessful.

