## 6.6. Reporting of Data After Early Discontinuation of IP

All participants who discontinued IP early are encouraged to stay in the study for continued assessments following the same study procedures until the EOS. Reasons for early IP discontinuation will be recorded. If a participant withdraws consent from continued monitoring, the EOS visit will be completed.

The purposes for collecting these data are to permit full efficacy data ascertainment per the ITT principle in accordance with the On-Study estimand and to allow continual monitoring of participant safety for the 4-week follow-up period after IP discontinuation.

Reporting rules for data collected after early discontinuation of IP are outlined for each data type (efficacy, safety, pharmacokinetic, pharmacodynamic, etc.) per the corresponding estimand, specifically the ICE handling strategy.

Safety data that are excluded from treatment emergent period, i.e., data collected after the 4-week follow-up post early discontinuation of IP, will be reported separately and will include basic summaries of:

- AE, SAEs and AESIs, (non-treatment emergent)
- Laboratory
- Concomitant medication.

Other collected safety data will be listed.

CONFIDENTIAL Page 37 of 139

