### 9.14. Summary of Data After Early Discontinuation of IP

All participants are encouraged to stay in the study regardless of IP discontinuation. Any participants who discontinue from IP will have their reason for discontinuing IP recorded and will continue in the study with their remaining scheduled study visits. The eCRF collection of data does not distinguish visits relative to IP termination milestone, therefore for the purpose of the analysis observations will be flagged if collected after IP early discontinuation. An additional timing variable will be introduced to reflect Study Day relative to EOT for visits occurring beyond treatment discontinuation.

Descriptive summaries will be presented for the subgroup of participants who discontinues IP early based on the available data through the EOS visit. For safety parameters these summaries will present data after 28 days following the last IP intake (>EOT+28 days). The summaries will be limited to the following assessments:

- AE, SAEs and AESIs,
- Laboratory and vital signs assessments.
- Deaths will be listed.

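### Severe periodontal disease triggers exit from the trial in Protocol 9.10.3.2 but only a stop of study drug, with continued follow-up, in Protocol 4.2.2.1

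*Protocol*

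**What the plan says.** Protocol Section 9.10.3.2 is mandatory and acts at trial level: "Subjects will be discontinued from the trial if they develop severe periodontal disease as defined by" pocket depth and attachment loss of at least 6 mm on two or more teeth, and Class 3 mobility or furcation involvement.

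Protocol Section 4.2.2.1 opens its list with "A subject may be discontinued from the study drug treatment before completion for any of the following reasons". Item 10 of that list is "Periodontal criteria met (see Section 9.10.3.2"), so both sections use the same criterion. The closing paragraph of 4.2.2.1 then covers everyone who stops study drug, except for consent withdrawal, death and loss to follow-up: "Every effort should be made by the Investigator to keep these subjects in the study through Visit 11".

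The rest of the plan takes the same line. Protocol 4.2.1: "All subjects are encouraged to stay in the study regardless of study treatment discontinuation". SAP 9.14 says participants who stop drug "will continue in the study with their remaining scheduled study visits". SAP 6.6 gives as one purpose of these data to "permit full efficacy data ascertainment per the ITT principle in accordance with the On-Study estimand". None of these places makes an exception for periodontal disease.

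**The concern.** The two sections give different instructions for one event. They differ in force (must against may) and in what is stopped (trial participation against study drug).

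The primary estimand handles early drug discontinuation by treatment policy (Protocol Table 1, SAP Table 1), so it relies on exacerbations observed after the drug is stopped. A literal reading of 9.10.3.2 makes those data missing by rule. Periodontal events are adverse events of special interest, and Protocol 9.10.3 says "AESIs are defined as events known as related to treatment with DPP1 inhibitors". Exits could therefore be more frequent on brensocatib than on placebo.

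There is also a safety cost. Table 5, footnote y, plans dental evaluation up to the end-of-study visit. SAP 9.3 tabulates the change in pocket depth from first to follow-up assessment. Early exit can cut both short in the most severe cases.

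**Working it through.** **Text comparison**

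| Place | Trigger | Action | Force |
|---|---|---|---|
| Protocol 9.10.3.2 | severe periodontal disease | leave the trial | mandatory |
| Protocol 4.2.2.1, item 10 | same, by cross-reference | stop study drug | permissive |
| Protocol 4.2.2.1, closing paragraph | any drug stop, three exceptions | stay through Visit 11 | every effort |
| Protocol 4.2.1; SAP 6.6 and 9.14 | any drug stop | stay in the study | encouraged or expected |

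Protocol 4.2.2 lets the investigator or sponsor withdraw a subject from the study. That is a case-by-case right and does not account for an automatic exit. The skin rule in 9.10.3.1 leaves the decision to the investigator and is not part of this point.

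**Inputs for the size** (Protocol 10.1): 540 per arm, placebo rate 1.2 per year, rate ratio 0.70 (so 0.84 per year on drug), dispersion 1, two-sided 0.005 per comparison, stated power 90%.

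**The plan's power.** Normal approximation, information per arm I = n·μ/(1+μ):
- I_b = 540 × 0.84/1.84 = 246.5; I_p = 540 × 1.2/2.2 = 294.5
- SE(log RR) = √(1/246.5 + 1/294.5) = 0.0863
- |ln 0.70|/SE − 2.807 = 4.132 − 2.807 = 1.325, giving 90.7%, in line with the stated 90%.

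**Loss per exit.** Years lost = (52 − w) × 7/365.25 for exit at week w. The expected exacerbations lost are this times 0.84 to 1.2.

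| Exit week | Years lost | Expected exacerbations lost |
|---|---|---|
| 4 | 0.92 | 0.77–1.10 |
| 16 | 0.69 | 0.58–0.83 |
| 28 | 0.46 | 0.39–0.55 |
| 40 | 0.23 | 0.19–0.28 |

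**Assumed range for the number of exits.** The documents give none. Phase 2 (Protocol 1.2.2.3) reports two study discontinuations for events of special interest, neither periodontal. Arm sizes follow from its percentages: 26/0.317 = 82 and 29/0.333 = 87, so 0 of 169 on brensocatib.
- One-sided 95% upper limit over 24 weeks: 1 − 0.05^(1/169) = 1.76%
- Over 52 weeks at constant hazard: 1 − (1 − 0.0176)^(52/24) = 3.77%
- Subjects per arm: 540 × 0.0377 = 20.3, so the range is 0 to about 20
- Person-time lost, with mean exit at 0.5 year (assumption): 20.3 × 0.5 = 10.2 years of 540, or 1.9%
- Exacerbations unobserved: 10.2 × 0.84 = 8.5 to 10.2 × 1.2 = 12.2, against 540 × 0.84 = 454 expected

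**Effect at that ceiling**
- Rate ratio, if all exits are on brensocatib and the rate off drug returns to the placebo rate: 0.70 × (1 − 0.0188) + 1 × 0.0188 = 0.706. The observed data would show 0.700, so the loss slightly favours the drug.
- Power, with exits at half of follow-up and the rate ratio held at 0.70: 90.5% with 3.77% exits on brensocatib only; 90.3% with 3.77% in both arms.

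**The case against.** The strongest counter-argument is that the documents can be read together. Item 10 points to 9.10.3.2 only for the criteria, the sentence opening the list supplies the consequence (stop drug), and the retention text governs what follows. The skin section uses similarly loose study-level wording for a criterion that is also on the drug-stop list, which suggests careless drafting. This is a fair account of the probable intent, but the wording of 9.10.3.2 is mandatory and names the trial, so a site following it would end participation.

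Other points stand in part:
- The retention request is in the closing paragraph of 4.2.2.1, not in item 10, and parts of the plan only encourage retention. The instructions still conflict.
- Emergency unblinding (Protocol 5.6) is another automatic study exit outside the three exceptions, so those exceptions are not a complete list of exits. But 5.6 does not also appear elsewhere as a drug-stop reason with follow-up to continue.
- Safeguards exist. Data up to exit count (SAP Table 5), an end-of-treatment visit is done (Protocol 4.2.2.2), and the adverse event is followed (4.2.2.1, 4.2.2.2). A missing-not-at-random tipping-point analysis runs if the main result is significant (SAP 6.2, 8.2.2), and a jump-to-reference analysis is planned if treatment-failure events are not trivial in number (SAP 8.2.4). These limit the damage but do not recover the data.
- An imbalance by arm is inferred from the mechanism; none is shown.

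**Conclusion.** The inconsistency is real: one criterion, linked by cross-reference, leads to mandatory exit from the trial in one section and to a drug stop with retention in another, and nothing in the documents resolves it. It deserves correction because the literal rule creates avoidable missing data where the estimand needs data, and shortens follow-up of a mechanism-related event.

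The size is small, and the primary conclusion is unlikely to change. The ceiling rests on a zero-event upper limit, a constant hazard from 24 to 52 weeks, mid-year exits, and full return to the placebo rate off drug. Phase 2's own exit rule is not in the documents, so the ceiling is indicative only; the true number of exits may be zero.

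**What to change.** In Protocol 9.10.3.2, change the action from leaving the trial to: *discontinued from study treatment, with continued study follow-up per Section 4.2.2.1*. The drug stop stays mandatory, and the three exceptions in 4.2.2.1 and the withdrawal right in 4.2.2 are untouched. Optionally, clarify in 9.10.3.1 that the investigator's decision after the dermatologist's evaluation concerns study treatment, keeping that discretion.

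At the blinded data review meeting already planned in SAP 6.2, list any subject who has left the study under this criterion, with exit date and follow-up lost. This overlaps with planned disposition and adverse event outputs (SAP 7.1, 9.2, 9.3), but adds the follow-up lost and makes it known before unblinding.

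The cost is one line of protocol text and one blinded listing, with no SAP change. Because the line is a safety-discontinuation rule, the sponsor must judge under Protocol 13.10 whether it needs an amendment with authority and ethics approval. The listing does not depend on that, and is worth having even if follow-up is too advanced for the text change to help.
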